Effectiveness of Salbutamol Administration by Nebulizer versus Metered Dose Inhaler in Acute Asthma in Children in Suez Canal University Hospital Emergency

Department: A Randomized Control Trial

March 10th 2018

Study Protocol

Study design

Single-blinded randomized control trial.

Study location

Pediatric Emergency Department in Suez Canal University Hospital.

Study population

This study includes patients presenting with an acute exacerbation of asthma at the Pediatric Emergency Department in Suez Canal University Hospital.

Inclusion criteria:

- Children ranging from 2 – 14 years old.
- Both genders will be included.
- Patients with an acute exacerbation of asthma who were previously diagnosed with asthma.

Exclusion criteria:

- Patients with arrhythmia and cardiac diseases.
- Patients with thyroid diseases.
- Patients with bronchiolitis or pneumonia.
- Patients with status asthmaticus requiring immediate pediatric intensive care unit hospitalization.

Sampling

All children fulfilling the inclusion criteria will be included consecutively until the calculated sample size had been reached.

Sample size

The sample size was calculated using the following formula:

$$n = 2 \left[\frac{(Z_{\alpha/2} + Z_{\beta}) * \sigma}{\mu_1 - \mu_2} \right]^2$$

Where:

n = sample size

$Z_{\alpha/2} = 1.96$ (The critical value that divides the central 95% of the Z distribution from the 5% in the tail)

$Z_{\beta} = 0.84$ (The critical value that separates the lower 20% of the Z distribution from the upper 80%)

σ = the estimate of the standard deviation = 1.5

μ_1 = mean in the nebulizer group = 4.4

μ_2 = mean in the metered-dose inhaler group = 3.3

Therefore, by calculation, the sample size was equal to 30 cases per group, giving a total sample size of 60 cases.

Methods of data collection

Infants and children known to have asthma coming to the Pediatric Emergency Department of Suez Canal University Hospital and fulfilling the inclusion criteria will be assessed according to the following clinical respiratory score:

Assess	Score 0	Score 1	Score 2
Respiratory Rate	<2 months <50 2-12 months <40 1-5 years <30 >5 years <20	<2 months 50-60 2-12 months 40-50 1-5 years 30-40 >5 years 20-30	<2 months >60 2-12 months >50 1-5 years >40 >5 years >30

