Patients will be reassessed after each treatment, if improved we can stop treatment and follow up after 2 hrs. Score <4 is considered a success while score>4 is failure of therapy. If not improved, we continue till the maximum number of treatment mentioned above.

Patients will be compared together according to the following characteristics: duration of treatment (preparation and delivery time), clinical outcome, patient satisfaction after treatment and hospitalization rate.

Each patient will have a form: Page 1 is an informed consent to be signed before randomization of treatment. Page 2 includes the following items that will be filled by parents after receiving the treatment;

1-personal data (name, age, address and telephone number). In addition, the researcher's phone number will be accessible to the patients.

2- Medical history (other illnesses, medications and degree of asthma either intermittent or persistent)

3-Clinical assessment (clinical respiratory score before and after treatment)

4-Patient satisfaction with given modality on a Likert scale from 1-5. This will be asked by the blinded assessor and included questions regarding:

- Comfort with modality used
- Duration of modality used
- Ease of administration
- Confidence in repeating treatment on their own at home if required

Statistical analysis of the data (Kotz et al, 2006)

Data will be fed to the computer and analyzed using IBM SPSS software package version 20.0. (Armonk, NY: IBM Corp) (Kirkpatrick, Feeney, 2013). Qualitative data will be described using number and percent. The Kolmogorov-Smirnov test is used to verify the normality of distribution. Quantitative data will be described using range (minimum and maximum), mean, standard deviation and median. Significance of the obtained results will be judged at the 5% level.

The used tests will be

1 - Chi-square test

For categorical variables, to compare between different groups (gender, address, satisfaction, admission)

2 - Fisher's Exact or Monte Carlo correction

Correction for chi-square when more than 20% of the cells have expected count less than 5

3 - Student t-test

For normally distributed quantitative variables, to compare between two studied groups (delivery and preparation time)

4 - Mann Whitney test

For abnormally distributed quantitative variables, to compare between two studied groups (age, percentage of improvement of clinical respiratory score and satisfaction).

Ethical Considerations

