- An informed consent will be obtained from legal guardian of all patients included in this study after full explanation of the aim of the study, benefits and hazards of the procedures.
- Standardized protocols are used for evaluation.
- The legal guardians have the right to withdraw without affecting the medical care expected to be offered to them.
- Confidentiality of all data and test results of all the study population will be preserved.
- The new modality introduced is a well-established form of administration and is not expected to cause any side effects that would not happen with the standard mode of administration (nebulizer).

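### No pulse rate, adverse event or drug side effect is recorded or compared, although the maximum nominal hourly salbutamol doses differ widely between arms, so the trial can say nothing about drug tolerability

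*Combined protocol and SAP*

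**What the plan says.** The Assessment section lists what will be compared between arms: "duration of treatment (preparation and delivery time), clinical outcome, patient satisfaction after treatment and hospitalization rate". The patient form holds personal data, medical history, the respiratory score before and after treatment, and four satisfaction questions. The statistical section assigns tests to gender, address, satisfaction, admission, preparation and delivery time, age and percentage improvement in the score. The score has six items: respiratory rate, auscultation, accessory muscles, mental status, room-air SpO2 and color.

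Other parts of the plan bear on drug effects. The exclusion criteria remove "Patients with arrhythmia and cardiac diseases", and also thyroid disease. The dosing section sets an hourly maximum in each arm. Ethical Considerations says that guardians will be told of hazards as well as benefits, and that the inhaler "is not expected to cause any side effects that would not happen with the standard mode of administration (nebulizer".

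**The concern.** Two regimens with very different maximum nominal doses are compared, and no variable for an unwanted effect of the drug is collected. The nearest item is the satisfaction question on comfort, which asks about the device.

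Three things are at stake.

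- If the two arms give similar scores, tolerability could be a reason to prefer one device, and the trial would have no data on it.
- If the scores differ, the cost in side effects would be unknown.
- The mental-status item gives 1 point for agitation. If salbutamol made a child agitated, that point would count as worse asthma. Because treatment continues, up to the stated maximum, in a child who has not improved, the point could also prolong exposure. With no pulse or event record, this could not be recognised afterwards.

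**Working it through.** **1. The plan's own sample size.** Inputs from the Sample size section: Z values 1.96 and 0.84, "the estimate of the standard deviation = 1.5", "mean in the nebulizer group = 4.4" and "mean in the metered-dose inhaler group = 3.3".

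n = 2 × [(1.96 + 0.84) × 1.5 / (4.4 − 3.3)]² = 2 × (4.2 / 1.1)² = 29.16, rounded up to 30 per group. Power at 30 per group is 0.811. The figure reproduces, and nothing below alters it.

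**2. Search for a safety variable.**

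| Place in the plan | Pulse rate, adverse event or drug side effect |
|---|---|
| Compared characteristics (Assessment) | none |
| Patient form | none; comfort refers to the device |
| Variables named in the tests | none |
| Six score items | none |

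**3. Maximum nominal hourly dose** (Dosage and administration).

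- Inhaler: 10 puffs × 0.1 mg = 1.0 mg, regardless of weight.
- Nebulizer: 3 × min(0.15 mg/kg × weight, 5 mg), that is 0.45 mg/kg up to 15 mg. The limit of 5 mg per administration is reached at 5 / 0.15 = 33.3 kg.

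The documents give ages 2 to 14 years but no weights, so the weights here are assumed.

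| Assumed weight | Nebulizer maximum per hour | Ratio to 1.0 mg |
|---|---|---|
| 10 kg | 4.5 mg | 4.5 |
| 11.1 kg | 5.0 mg | 5.0 |
| 12 kg | 5.4 mg | 5.4 |
| 20 kg | 9.0 mg | 9.0 |
| 30 kg | 13.5 mg | 13.5 |
| 33.3 kg and above | 15 mg | 15 |

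The ceiling of 15 follows from the documents alone. The lower end of about 5 needs a weight of at least 5 / 0.45 = 11.1 kg.

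Sensitivity of the ratio:

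- If the 5 mg limit were meant per hour, the ratio would be about 5 at every weight from 11.1 kg.
- If a child stopped after one nebulization and the comparison were a full inhaler course, the ratio would run from 1.5 (10 kg) to 5 (33.3 kg and above).

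**4. Effect on the score.** The mental-status item gives 0 for normal to mildly irritable, 1 for agitation and 2 for lethargy. Agitation can therefore add at most 1 of 12 points, and only in a child who would otherwise score 0 on that item. One point can move a total from 3, a success, to 4, which is not. If percentage improvement means (before − after) / before, which the plan does not define, 1 point is worth 1/4 = 25 percentage points at a baseline of 4 and 1/12 = 8.3 at a baseline of 12.

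**5. What 30 per arm could show if the data were collected.**

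- Pulse change, 95% CI half-width: about 2.00 × √(2/30) = 0.52 SD.
- Pulse change, difference detectable with 80% power: (1.96 + 0.84) × √(2/30) = 0.72 SD. The documents give no SD for pulse.
- No events in 30 children: one-sided 95% upper bound 1 − 0.05^(1/30) = 9.5%.
- Power at assumed event rates: 39% for 40% against 20%, 69% for 50% against 20%, and 49% for 30% against 10%. The documents give no event rates.

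**The case against.** The trial is titled and sized as a study of effectiveness, and tolerability is not a stated aim. That stands: the omission breaks no promise of the plan and biases none of its planned comparisons by itself.

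A reader might infer more than the text supports, in four ways.

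- **That the protocol claims the inhaler adds no side effects and the trial fails to test the claim.** The sentence is an expectation in the ethics section, limited to effects not already seen with the nebulizer. It is neither a hypothesis nor a planned conclusion.
- **That the dose gap contradicts that expectation.** The larger nominal dose is in the nebulizer arm, so a lower-dose inhaler is consistent with the sentence. The gap shows only why a comparison would be informative.
- **That agitation could move the score by 2 points.** In the score table 2 is lethargy; agitation is 1. How often the drug would cause agitation is not given.
- **That only benefit is compared.** Time, satisfaction and admission are compared too.

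There is also a fair objection to collecting the data. Parents complete page 2 of the form and know the device, so events that they report are unblinded. Palpitations are hard to elicit from the youngest children. The nebulizer is driven by oxygen, so a difference in pulse would not isolate the effect of the drug. These points limit what the data could prove, but they do not make recording nothing the better choice.

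**Conclusion.** The point holds as a gap in what the trial can conclude. No variable for a drug side effect is recorded or compared, while the maximum nominal hourly doses are up to 0.45 mg/kg (15 mg from 33.3 kg) against 1.0 mg. The range of about 5- to 15-fold rests on assumed weights of about 11 kg or more and on reading the 5 mg limit as per administration. It compares maxima, so it describes neither doses received nor drug reaching the lung.

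As planned, the trial can report on score, time, satisfaction and admission. It can say nothing about drug tolerability, and it cannot examine the expectation stated under Ethical Considerations. A 1-point rise in the score from drug-related agitation is possible but of unknown frequency. The gap should be closed because this is cheap; it does not threaten the sample size or the planned efficacy comparison. No view is taken on which dose is right.

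**What to change.** - Have the blinded assessor write down the pulse rate at each SpO2 reading already taken for the score, before and after treatment. This assumes that SpO2 is read with a pulse oximeter that shows pulse rate.
- Add one yes/no line to the form for tremor and vomiting, and for palpitations where the child can report them. State who answers it.
- Pre-specify one descriptive table: the between-arm difference in pulse change with a 95% CI, and the number of children in each arm with any event. State that a non-significant difference will not be read as equal safety.
- If these are not added, limit the conclusions to score, time, satisfaction and admission.

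The cost is one number per existing reading, one form line and one table, with no extra visit, procedure or staff. The report should state the limits: low precision at 30 per arm, unblinded parental reporting, and the oxygen-driven nebulizer as another possible source of a pulse difference. The change adds measurement only and sets no dose or treatment threshold.
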